5.7. Investigational Product Accountability

The investigative site must maintain adequate records documenting the receipt, use, loss, or other disposition of the investigational product supplies. To ensure adequate records, all drug supplies will be accounted for in the drug accountability inventory forms as instructed by Pfizer and will be monitored by the accounting of unused investigational product returned

by the subjects. At the end of the clinical trial, all drug supplies unallocated or unused by the subjects must be returned to Pfizer or its appointed agent, or destroyed in an approved manner unless otherwise authorized by Pfizer. In either case, the forms must identify the investigational product, including batch or code numbers, and account for its disposition on a subject-by-subject basis, including specific dates and quantities.

The sponsor or designee will provide guidance on the destruction of unused investigational product (eg, at the site). If destruction is authorized to take place at the study site, the investigator must ensure that the materials are destroyed in compliance with applicable environmental regulations, institutional policy, and any special instructions provided by Pfizer and all destruction must be adequately documented. All bottles must be returned to the investigator by the subject.

5.7.1. Destruction of Investigational Product Supplies

The sponsor or designee will provide guidance on the destruction of unused investigational product (eg, at the site). If destruction is authorized to take place at the study site, the investigator must ensure that the materials are destroyed in compliance with applicable environmental regulations, institutional policy, and any special instructions provided by Pfizer, and all destruction must be adequately documented.

5.8. Concomitant Treatment(s)

Subjects will abstain from all concomitant medications as described in the [Inclusion](#) and [Exclusion Criteria](#) sections of the protocol.

Medications that are taken in the Screening/Washout period (after informed consent is obtained and before the first dose of study drug) will be documented as prior medications. Medications taken after the first dose of study drug has been administered will be documented as concomitant medications. All concomitant medications taken during the study must be recorded in study records with indication, daily dose, and start and stop dates of administration. Subjects will be queried about concomitant medication (including topical medications and treatments, over-the-counter and prescription medications and treatments, and vaccinations) at each study visit. Any new concomitant medications or dose changes to current concomitant medications should be evaluated for potential new or worsening adverse events.

The start date, stop date, and indication for all therapies will be recorded on the CRF.

5.8.1. Permitted Concomitant Medications

The following concomitant AD therapies are permitted during the study:

- Oral antihistamines.
- Subjects will be provided a non-medicated study emollient and a sunscreen at the Screening visit. Subjects will start the emollient 7 days prior to Day 1 through to the follow up visit and use the sunscreen as needed. The non-medicated study emollient

and sunscreen are the only topical products permitted to be used on atopic dermatitis skin during the study. If a subject has a history of intolerability or currently does not tolerate the non-medicated study emollient or sunscreen or if the product is unavailable, the investigator should contact the Pfizer clinician or designee for approval to use an alternative topical treatment; the approved alternative non-medicated emollient and sunscreen should be documented in study records.

A subject who is receiving a permitted concomitant medication for any reason must be on a locally-approved medication and dose for the treated indication, and this must be documented in the CRF. Subjects are not allowed any other investigational drugs or treatments during the study.

Subjects should refrain from starting new or changing doses of permitted prescription or non-prescription drugs, vitamins, and dietary supplements within 7 days or 5 half-lives (whichever is longer) prior to Day 1 and prior to study visits throughout the study, unless otherwise noted below.

Acetaminophen may be used intermittently (not to exceed 1 g/day). Vitamin and mineral supplements of standard potency are allowed in amounts not known to be associated with adverse effects (such as hypervitaminosis).

Subjects should report any changes to permitted medications during the study to the investigator as soon as they occur. Medication changes must be documented in the subject's record and CRF.

Unless a prohibited medication or treatment, subjects may be administered any other medications necessary for the treatment of concomitant medical disorders as deemed necessary by the treating physician. Following Day 1, addition of concomitant medications or any change in the dosage should be limited to those considered medically essential.

5.8.2. Prohibited Medications and Treatments

Subjects are required to discontinue and avoid using certain medications and treatments (see [Inclusion/Exclusion Criteria](#) and [Appendix 3](#)). Subjects should be instructed at each visit to contact the study site investigator promptly if there are any intended changes or additions to concomitant medications.

All medications and treatments that could affect atopic dermatitis must be discontinued except oral antihistamines. Due to the potential to affect atopic dermatitis with ultraviolet light exposure, subjects must also avoid prolonged exposure to the sun and avoid the use of tanning booths, sun lamps or other ultraviolet light sources during the study.

For the purposes of this protocol, dietary supplements are defined as vitamins, minerals, purified food substances, and herbals with pharmaceutical properties. Vitamins, minerals and purified food substances are allowed in amounts not known to be associated with adverse effects (such as hypervitaminosis).

Herbals supplements are only allowed on a case by case basis; please contact the Pfizer staff. Herbal medications with unknown properties or known beneficial effects for AD or that are known to have an effect on drug metabolism (eg St. John's Wort) must be discontinued at least 1 week or 5 half-lives (whichever is longer) before the first dose of investigational product.

Restrictions on certain vaccinations are described in [Section 5.8.3](#).

5.8.3. Vaccinations

Vaccination with live virus, attenuated live virus, or any live viral components is prohibited within the 6 weeks prior to the first dose of study drug, during the study, and for 6 weeks after the last dose of investigational product. Similarly, current routine household contact with individuals who have been vaccinated with live vaccine components should be avoided during treatment and for 6 weeks following completion of treatment.

Such vaccines include: FluMist[®] (intranasal influenza vaccine), attenuated rotavirus vaccine, varicella (chickenpox) vaccine, attenuated typhoid fever vaccine, oral polio vaccine, MMR (measles, mumps, rubella) vaccine and vaccinia (smallpox) vaccine. Following vaccination with live component vaccines, the virus may be shed in bodily fluids, including stool, and there is a potential risk that the virus may be transmitted.

6. STUDY PROCEDURES

Refer to the [Schedule of Activity](#) for a detailed list of a detailed list of study procedures as they should be conducted at each respective visit. Visit windows are based on Day 1 visit.

Subjects are required to fast for at least 8 hours prior to all visits that include lipid profile panel testing (Day 1, Week 6, Week 12, and EOS). During the fasting period, subjects should refrain from all food and liquids (water and non-study medications are permitted).

Due to possible need for PPD testing and chest radiograph, screening procedures may be performed over more than 1 visit in the 35 days prior to the Day 1 visit.

Visits should occur in the morning and prior to the subject's dose on Day 1, Week 6, Week 12, and EOS. To assure consistency and reduce variability, all study visits should occur in the morning whenever possible. On days of study visits, subjects will receive their dose at the clinic during their study visit.

Urine pregnancy test must be performed prior to dosing with the investigational product for female subjects of childbearing potential through to the EOS visit.

Non-medicated study emollient and sunscreen will be provided to subjects at the Screening Visit and re-supplied during the study as applicable. Prior to attending a study visit, subjects are allowed to shower but should not moisturize. However, they may apply study provided emollient upon completion of all clinic visit study procedures. Subjects will start the study provided emollient 7 days prior to Day 1 through to the EOS visit.

Refer to [Appendix 11](#) for guidelines on subject safety monitoring and discontinuation.

6.1. Visit 1, Screening

Subjects will be screened within 35 days prior to administration of the investigational product to confirm that they meet the subject selection criteria for the study. The investigator (or an appropriate delegate at the investigator site) will obtain informed consent from each subject in accordance with the procedures described in the [Subject Information and Consent](#) section.

If the Mantoux PPD tuberculin skin test is given, the subject must return between 48-72 hours post-injection for induration evaluation.

Screening laboratory tests with abnormal results may be repeated once to confirm abnormal results; the last value will be used to determine eligibility. If results return to normal within the 5-week screening period, the subject may enter the study. Sites will be permitted to re-screen subjects (with a new screening number) who initially do not meet eligibility criteria once.

The following procedures will be completed:

- Obtain written informed consent.
- Review Inclusion and Exclusion criteria.
- Register subject in Impala.
- Demography.
- Complete medical history, including history of drug, alcohol and tobacco use. Smoking status and average weekly alcohol consumption (units/week) will also be collected, where a unit contains 12 g of pure alcohol, an amount equivalent to that contained in 5 oz (a glass) of wine, 12 oz of beer, or 1.5 oz of 90 proof of spirits.
- Complete AD disease history includes collection of details of AD: AD diagnosis, the use of topical treatments, systemic treatments and other treatments for AD.
- Obtain complete medication history of all prescription or nonprescription drugs, and dietary and herbal supplements taken within 35 days prior to the planned first dose.

The following timeframes prior to the planned first dose must be used for collection of the following Current/Prior Medications:

- 2 years: Lipid-lowering medications;
- 3 years: Previous drug treatments for AD includes use of topical treatments, systemic treatments and other any treatments.

- Conduct complete physical examination.
- Obtain vital signs including pulse rate, blood pressure, respiratory rate (after at least 5 minutes of rest) and oral or tympanic temperature.
- Obtain weight
- Obtain height.
- Chest X-ray (if previous chest X-ray has not been performed within 12 weeks of Day 1, may require a visit to a different location).
- Perform single 12-lead electrocardiogram (ECG).
- Obtain samples for laboratory testing: Blood chemistry, hematology, urinalysis, serum FSH or pregnancy test, HIV, HBsAg, HBcAb, and HCVAb.
- Mantoux Purified Protein Derivative (PPD) skin test or QuantiFERON[®] – TB Gold test (unless performed within 12 weeks of Day 1). If Mantoux PPD tuberculin skin test is performed, the subject must return between 48-72 hours post-injection for evaluation of induration.
- Conduct clinical evaluations including IGA, EASI, BSA, and SCORAD.
- Dispense ePRO handheld device. CCI will be collected daily in selected country/ies daily starting 3 days prior to Day 1 through to the End of Study visit.
- Dispense study emollient and sunscreen. Subjects will start the emollient 7 days prior to Day 1 through to the end of study visit.
- Assess for occurrence of Adverse Events: The SAE reporting period starts with the signing of the informed consent.

6.2. Study Period

6.2.1. Visit 2, Day 1/Week 0

- Review of Inclusion/Exclusion Criteria.
- If subject meets all Inclusion/Exclusion criteria, officially randomize subject into the study.
- Review any changes in the subject's prior and concomitant treatment information.
- Obtain vital signs including pulse rate, blood pressure, respiratory rate (after at least 5 minutes of rest) and oral or tympanic temperature.
- Obtain weight.

- Conduct complete physical examination.
- Obtain **fasting** samples for blood chemistry including lipid profile.
- Obtain samples for other laboratory testing: hematology, urinalysis, urine pregnancy test (female subjects of childbearing potential only), EBV, CMV, HSV1, HSV2, VZV, IgE, hsCRP, IP-10, IL-31, CCL17, TBNK, T cell subsets, and exploratory biomarker samples.
- Perform Fitzpatrick skin type assessment.
- Photography (at selected sites).
- Conduct clinical evaluations including IGA, EASI, BSA, and SCORAD.
- Administer PROs including Pruritus NRS, PtGA, DLQI, POEM, and HADS.

Note: The Pruritus NRS will be assessed daily from Day 1 to 15.

- Review CCI (in selected country/ies) as necessary.
- Perform single 12-lead ECG.
- Obtain Prep D1 sample for banked biospecimen pharmacogenomics testing.
- Confirm proper contraception is being used.
- Administer first dose of study drug to subject.
- Dispense study drug supply to the subject.
- Assess for occurrence of Adverse Events by spontaneous reporting of adverse events and by asking the subjects to respond to a non-leading question such as “How do you feel?”

6.2.2. Visit 3, Day 8/Week 1 (± 1 day)

- Conduct targeted physical examination.
- Obtain vital signs including pulse rate, blood pressure, respiratory rate (after at least 5 minutes of rest) and oral or tympanic temperature.
- Obtain samples for laboratory testing: hematology and urine pregnancy test (female subjects of childbearing potential only).
- Conduct clinical evaluations including IGA, EASI, BSA, and SCORAD.

- Administer PROs including Pruritus NRS, PtGA, DLQI, POEM, and HADS.

Note: The Pruritus NRS will be assessed daily from Day 1 to 15.

- Review CCI (in selected country/ies) as necessary.
- Confirm proper contraception is being used.
- Review any changes in the subject's concomitant treatments information.
- Perform drug accountability procedures.
- Administer study drug to the subject.
- Dispense study drug to the subject.
- Assess for occurrence of Adverse Events by spontaneous reporting of adverse events and by asking the subjects to respond to a non-leading question such as "How do you feel?"

6.2.3. Visit 4, Day 15/Week 2 (±1 day)

- Conduct targeted physical examination.
- Obtain vital signs including pulse rate, blood pressure, respiratory rate (after at least 5 minutes of rest) and oral or tympanic temperature.
- Obtain samples for laboratory testing: blood chemistry, hematology, urine pregnancy test (female subjects of childbearing potential only), IgE, hsCRP, CXCL-10, IL-31, CCL17, TBNK, and T cell subsets.
- Obtain samples for PK analysis prior to dosing.
- Conduct clinical evaluations including IGA, EASI, BSA, and SCORAD.
- Administer PROs including Pruritus NRS, PtGA, DLQI, POEM, and HADS.
- Review CCI (in selected country/ies) as necessary.
- Confirm proper contraception is being used.
- Review any changes in the subject's concomitant treatments information.
- Perform drug accountability procedures.
- Administer study drug to the subject.

- Dispense study drug to the subject.
- Assess for occurrence of Adverse Events by spontaneous reporting of adverse events and by asking the subjects to respond to a non-leading question such as “How do you feel?”

6.2.4. Visit 5, Day 29/Week 4 (±1 day)

- Conduct targeted physical examination.
- Obtain vital signs including pulse rate, blood pressure, respiratory rate (after at least 5 minutes of rest) and oral or tympanic temperature.
- Obtain samples for laboratory testing: hematology, urine pregnancy test (female subjects of childbearing potential only), IgE, hsCRP, IP-10, IL-31, CCL17, TBNK, T cell subsets, and exploratory biomarker samples.
- Obtain samples for PK analysis prior to dosing.
- Conduct clinical evaluations including IGA, EASI, BSA, and SCORAD.
- Administer PROs including Pruritus NRS, PtGA, DLQI, POEM, and HADS.
- Review CCI (in selected country/ies) as necessary.
- Confirm proper contraception is being used.
- Review any changes in the subject’s concomitant treatments information.
- Perform drug accountability procedures.
- Administer study drug to the subject.
- Dispense study drug to the subject.
- Assess for occurrence of Adverse Events by spontaneous reporting of adverse events and by asking the subjects to respond to a non-leading question such as “How do you feel?”

6.2.5. Visit 6, Day 43/Week 6 (±1 day)

- Conduct targeted physical examination.
- Obtain vital signs including pulse rate, blood pressure, respiratory rate (after at least 5 minutes of rest) and oral or tympanic temperature.
- Obtain **fasting** samples for blood chemistry including lipid profile.

- Obtain samples for laboratory testing: hematology, urinalysis, urine pregnancy test (female subjects of childbearing potential only), EBV, CMV, HSV1, HSV2, VZV, IgE, hsCRP, IP-10, IL-31, CCL17, TBNK, and T cell subsets.
- **Prior to dosing**, obtain samples for PK analysis (the first PK sample is to be collected 2 hours (± 30 minutes) prior to dosing; the second PK sample is to be collected immediately prior to dosing).
- Photography (at selected sites).
- Conduct clinical evaluations including IGA, EASI, BSA, and SCORAD.
- Administer PROs including Pruritus NRS, PtGA, DLQI, POEM, and HADS.
- Review CCI (in selected country/ies) as necessary.
- Confirm proper contraception is being used.
- Review any changes in the subject's concomitant treatments information.
- Perform drug accountability procedures.
- Administer study drug to the subject.
- Obtain samples for PK analysis at 0.5 hour (± 15 minutes) after dosing.
- Dispense study drug to the subject.
- Assess for occurrence of Adverse Events by spontaneous reporting of adverse events and by asking the subjects to respond to a non-leading question such as "How do you feel?"

6.2.6. Visit 7, Day 57/Week 8 (± 3 day)

- Conduct targeted physical examination.
- Obtain vital signs including pulse rate, blood pressure, respiratory rate (after at least 5 minutes of rest) and oral or tympanic temperature.
- Obtain samples for laboratory testing: hematology and urine pregnancy test (female subjects of childbearing potential only), IgE, hsCRP, IP-10, IL-31, CCL17, TBNK, T cell subsets, and exploratory biomarker samples.
- Obtain samples for PK analysis prior to dosing.
- Photography at selected sites (at PI's discretion).

- Conduct clinical evaluations including IGA, EASI, BSA, and SCORAD.
- Administer PROs including Pruritus NRS, PtGA, DLQI, POEM, and HADS.
- Review **CCI** (in selected country/ies) as necessary.
- Confirm proper contraception is being used.
- Review any changes in the subject's concomitant treatments information.
- Perform drug accountability procedures.
- Administer study drug to the subject.
- Dispense study drug to the subject.
- Assess for occurrence of Adverse Events by spontaneous reporting of adverse events and by asking the subjects to respond to a non-leading question such as "How do you feel?"

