	1	2	3	4	5	6	7	8	9	10	11
Visit Identifier	1	2	3	4	5	6	7	8	9	10	11
Visit Day/Week	Days -35 to -1	Day 1/ W 0	Day 8/ W 1	Day 15/ W 2	Day 29/ W 4	Day 43/ W 6	Day 57/ W 8	Day 85/ W 12	Day 92/ W 13	Day 99/ W 14	Day 113/W 16 ET/EOS
Visit Window ^a	None	None	±1 Day based on Day 1 visit				±3 Days based on Day 1 visit		±3 Day based on Day 1 visit		
Enrollment Procedure											
Informed Consent	X										
Inclusion/Exclusion Criteria	X	X									
Demographics, Medical History, Atopic Dermatitis Disease History ^b	X										
Medical Procedures											
Complete Physical Exam ^c	X	X						X			X
Targeted Physical Exam ^c			X	X	X	X	X		X	X	
Vital Signs ^d	X	X	X	X	X	X	X	X	X	X	X
Weight	X	X									X
Height	X										
Chest X-ray ^e	X										
ECG (12 lead)	X	X						X			X
Laboratory Assessments											
Blood Chemistry ^f	X	X		X		X		X		X	X
Urinalysis	X	X				X		X			X
Hematology	X	X	X	X	X	X	X	X	X	X	X
Serum FSH (WONCBP only) or Pregnancy Test ^g	X										
Urine Pregnancy Test (conducted at study site) ^h		X	X	X	X	X	X	X	X	X	X

Protocol Activity	Screening	Treatment Period							Follow-up Period		
		1	2	3	4	5	6	7	8	9	10
Visit Identifier	Days -35 to -1	Day 1/ W 0	Day 8/ W 1	Day 15/ W 2	Day 29/ W 4	Day 43/ W 6	Day 57/ W 8	Day 85/ W 12	Day 92/ W 13	Day 99/ W 14	Day 113/W 16 ET/EOS
Visit Window ^a	None	None	±1 Day based on Day 1 visit				±3 Days based on Day 1 visit		±3 Day based on Day 1 visit		
HIV Testing (per local regulations) ⁱ	X										
HBsAg, HBcAb, and HCVAb (HepB reflex testing) ^j	X										
Tuberculosis test ^k	X										
Viral Surveillance: EBV, CMV, HSV1, HSV2, and VZV		X				X		X			X
Laboratory Pharmacodynamics											
Total IgE		X		X	X	X	X	X			X
hsCRP		X		X	X	X	X	X			X
IP-10 (CXCL10)		X		X	X	X	X	X			X
IL-31		X		X	X	X	X	X			X
CCL17 (TARC)		X		X	X	X	X	X			X
FACS-TBNK and T cell Subsets		X		X	X	X	X	X			X
Blood for mRNA exploratory analysis		X			X		X	X			X
Serum for exploratory analysis		X			X		X	X			X
Cell-free plasma for exploratory analysis		X			X		X	X			X
Pharmacokinetic											
Pharmacokinetic Sampling (Pre-dose only) ^l				X	X		X				
Pharmacokinetic Sampling ^m						X		X			
Trial Treatment											
Impala Registration	X										
Randomize Subjects in IWRS		X									
Drug Dispensing		X	X	X	X	X	X				
Drug Accountability			X	X	X	X	X	X			
Investigational Treatment Administrationⁿ		X-----X									
Emollient and Sunscreen Dispensing ^o	X										

090177e18dabc380\0.1\Draft\Versioned On:07-Feb-2018 09:59 (GMT)

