- f. Blood Chemistry consists of blood urea nitrogen (BUN), serum creatinine, creatine phosphokinase, glucose, Ca⁺⁺, Na⁺, K⁺, Cl⁻, total CO₂, aspartate aminotransferase (AST), alanine aminotransferase (ALT), total and direct bilirubin, alkaline phosphatase, uric acid, albumin, total protein, and lipid profile panel. Lipid profile panel will include total cholesterol, low-density lipoprotein (LDL), high-density lipoprotein (HDL), and triglycerides. A minimum of 8-hour fasting is required for lipid profile evaluation at Day 1, W 6, W 12, and EOS. **Laboratory tests may be repeated once during the screening period;** the last value will be used to determine eligibility.
- g. Serum pregnancy testing at screening is required for women of childbearing potential. Follicle stimulating hormone (FSH) test to be performed at Screening to confirm postmenopausal status in female subjects who have been amenorrheic for at least 12 consecutive months.
- h. Urine pregnancy test must be performed prior to dosing with the investigational product for female subjects of childbearing potential.
- i. Subjects who are positive for HIV will be screen-failed.
- j. All subjects will be screened for HBsAg and HBcAb; subjects who are HBsAg positive will be screen-failed. Subjects who are HBsAg negative but HBcAb positive will be reflex-tested for HBsAb and, if HBsAb positive, may enroll; if HBsAb negative, they will be screen-failed. Subjects who are positive for HCVAb will be screen-failed.
- k. A documented TB test performed within 12 weeks prior to Day 1 is acceptable. IGRA official reading and method, or test as per country specific guidelines, must be located in source documentation. Subjects with a history of tuberculosis may not require TB testing as per the protocol [Section 4.2](#).
- l. Pharmacokinetic samples will be collected at the following visits prior to dosing at the study site on: Week 2, 4 and 8.
- m. On Week 6, PK samples will be collected at 2 hour (±30 min) pre-dose, immediately prior to dosing, and 0.5 hour (±15 min) post dose. On Week 12, PK samples will be collected at 2 hour (±30 min) pre-dose, immediately prior to dosing, and 1 hour (±30 min), 2 hour (±30 min) and 4 hour (±30 min) post dose.

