In the definitive EFD study in rats, the maternal NOAEL was 60 mg/kg/day and, based on decreased embryo-fetal survival at 60 mg/kg/day and increased incidence of skeletal variations at 30 and 60 mg/kg/day, the developmental NOAEL was 10 mg/kg/day. In the definitive EFD study in rabbits, the maternal and developmental NOAEL was the highest dose tested, 75 mg/kg/day.

Although PF-04965842 absorbs light in the UVB/visible range, no evidence of cutaneous or ocular phototoxicity was noted after oral administration to pigmented Long-Evans rats followed by a single exposure to ultraviolet radiation (UVR). Therefore, PF-04965842 does not have significant phototoxicity potential in vivo.

In the liver, PF-04965842-related minimal to mild increases in serum transaminases (alanine aminotransferase [ALT] and aspartate aminotransferase [AST]) occurred in the 7-day, 1-month, and 6-month studies in rats (at 70 mg/kg/day) and in the 1-month study in cynomolgus monkeys (at ≥ 40 mg/kg/day). In the 1-month study, increased liver weights occurred in rats (at 200 mg/kg/day) and cynomolgus monkeys (at ≥ 80 mg/kg/day) and periportal hepatocyte hypertrophy occurred in rats at 200 mg/kg/day. However, there were no microscopic changes in the liver in any study in rats or cynomolgus monkeys that were consistent with hepatocyte degeneration, necrosis, or inflammation, and as such these findings in serum hepatic enzymes were not considered adverse.

Physal dystrophy was observed in the 1-month study in rats at ≥ 75 mg/kg/day and was consistent with test article-related effects on bone growth in young, growing rats during a rapid period of growth. No microscopic findings in the bone physis were observed in the 6-month toxicity study in rats or 1-month or 9-month toxicity studies in cynomolgus monkeys. Since the growth plate is closed (inactive) in the adult humans, the finding of the physal dystrophy of the growth plate in rats would not be expected to pose any risk to subjects in the planned clinical trials.

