6.2.7. Visit 8, Day 85/Week 12 (± 3 day)

- Conduct complete physical examination.
- Obtain vital signs including pulse rate, blood pressure, respiratory rate (after at least 5 minutes of rest) and oral or tympanic temperature.
- Obtain **fasting** samples for blood chemistry including lipid profile.
- Obtain samples for laboratory testing: hematology, urinalysis, urine pregnancy test (female subjects of childbearing potential only), EBV, CMV, HSV1, HSV2, VZV, IgE, hsCRP, IP-10, IL-31, CCL17, TBNK, T cell subsets, and exploratory biomarker samples.
- **Prior to dosing**, obtain samples for PK analysis (the first PK sample is to be collected 2 hours (± 30 minutes) prior to dosing; the second PK sample is to be collected immediately prior to dosing).
- Photography at selected sites (at PI's discretion).
- Conduct clinical evaluations including IGA, EASI, BSA, and SCORAD.
- Administer PROs including Pruritus NRS, PtGA, DLQI, POEM, and HADS.
- Review **CCI** (in selected country/ies) as necessary.
- Perform single 12-lead ECG.

- Confirm proper contraception is being used.
- Review any changes in the subject's concomitant treatments information.
- Perform drug accountability procedures.
- Administer study drug to the subject.
- Obtain samples for PK analysis at 1 hour (± 30 minutes), 2 hour (± 30 minutes), and 4 hour (± 30 minutes), after dosing.
- Assess for occurrence of Adverse Events by spontaneous reporting of adverse events and by asking the subjects to respond to a non-leading question such as "How do you feel?"

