6.3. Follow-up Visits

6.3.1. Visit 9, Day 92/Week 13 (± 3 day)

- Conduct targeted physical examination.
- Obtain vital signs including pulse rate, blood pressure, respiratory rate (after at least 5 minutes of rest) and oral or tympanic temperature.
- Obtain samples for laboratory testing: hematology and urine pregnancy test (female subjects of childbearing potential only).
- Conduct clinical evaluations including IGA, EASI, BSA, and SCORAD.
- Review CCI (in selected country/ies) as necessary.
- Confirm proper contraception is being used.
- Review any changes in the subject's concomitant treatments information.
- Assess for occurrence of Adverse Events by spontaneous reporting of adverse events and by asking the subjects to respond to a non-leading question such as "How do you feel?"

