Appendix 11.2. Discontinuation

Treatment with PF-04965842 will be discontinued and the subject withdrawn from this study for:

Adverse Events:

- Serious infections, defined as any infection (viral, bacterial, and fungal) requiring parenteral antimicrobial therapy or hospitalization;
- Other serious or severe AEs, after consultation with the Pfizer clinician.

Laboratory Abnormalities:

All the following laboratory abnormalities **require discontinuation** if they are confirmed. Confirmation through re-testing should occur within 1 week:

Laboratory Variable	Laboratory Value
Hematology	
Absolute Neutrophil Count	<1000/mm ³ ; <1.0 x10 ⁹ /L
Hemoglobin	<10.0 g/dL; <6.2 mmol/L; <100 g/L
Platelet count	<75,000/mm ³ ; <75.0x10 ⁹ /L
Lymphocytes	<500/mm ³ ; <0.8x10 ⁹ /L
Chemistry	
AST	>2.5x ULN
ALT	>2.5x ULN
Creatinine (serum)	>1.5x ULN
Total bilirubin ^a	>1.5x ULN

^a Total bilirubin ≥1.5 x ULN; subjects with a history of Gilbert's syndrome may have a direct bilirubin measured and would be eligible for this study provided the direct bilirubin is ≤ ULN

The following vital sign abnormality will **require discontinuation** if it is confirmed. Confirmation through re-testing should occur within 1 week:

- Diastolic: recurrent or persistent (≥24 hrs) or symptomatic increase from baseline, in same posture, by >20 mmHg.

Discontinuation/End of Treatment Monitoring for Adverse Events, Laboratory, and Vital Signs:

Any subject meeting discontinuation criteria must enter into the Follow-up Period with their first follow-up visit occurring 1 week after their last dose, until the event has returned to normal or baseline levels or is deemed clinically stable. The only exception to this is when a subject specifically withdraws consent for any further contact with him or her or persons previously authorized by the subject to provide this information. Additional follow-up visits may occur as needed until any clinically relevant abnormalities or adverse events have resolved, returned to a baseline state, or are deemed clinically stable.

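### No blood chemistry is scheduled for 42 days of dosing (Day 43 to Day 85), so after about Day 50 only an unscheduled test can trigger the AST, ALT, creatinine and bilirubin stop rules before the last planned dose

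*Protocol*

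**What the plan says.** Protocol Appendix 11.2 lists eight laboratory rows that require discontinuation if confirmed. Four are hematology (neutrophils, hemoglobin, platelets, lymphocytes) and four are chemistry (AST, ALT, serum creatinine, total bilirubin). On confirmation it says: "Confirmation through re-testing should occur within 1 week".

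The four chemistry analytes all belong to the blood chemistry panel. Footnote f of the Schedule of Activities includes serum creatinine and "aspartate aminotransferase (AST), alanine aminotransferase (ALT), total and direct bilirubin, alkaline phosphatase". The row "Blood Chemistry ^f" is marked at Screening, Day 1, Weeks 2, 6, 12 and 14, and Week 16 or early termination. It is blank at Weeks 1, 4, 8 and 13. The visit lists in sections 6.2 and 6.3 agree with it.

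Blood is nevertheless drawn at the visits in between. Week 4 (section 6.2.4) reads "Obtain samples for laboratory testing: hematology, urine pregnancy test (female subjects of childbearing potential only), IgE, hsCRP, IP-10, IL-31, CCL17" and Week 8 (section 6.2.6) reads "Obtain samples for laboratory testing: hematology and urine pregnancy test (female subjects of childbearing potential only), IgE, hsCRP, IP-10, IL-31, CCL17". Both go on to cell subsets and exploratory biomarkers and add a pre-dose PK sample. Neither includes chemistry. Hematology is marked at every visit.

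Dosing runs from Day 1 to Day 85 (Schedule of Activities, footnote n). At Week 12 (section 6.2.7) the chemistry sample is taken at the same visit as the last planned dose: "Administer study drug to the subject".

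Unscheduled laboratory tests are allowed at any time, for a perceived safety concern, by section 7.5.2 and by the opening of Appendix 11.

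**The concern.** A mandatory stop rule protects a patient only if its analyte is read while there is still dosing to stop. For the four chemistry rows the longest interval without a scheduled reading is the last one, and the sample that closes it is taken on the last dosing day. A patient whose AST, ALT, creatinine or bilirubin crosses a limit after the Week 6 sample could take drug for up to six more weeks unless something prompts an extra test. A rise without symptoms may prompt nothing.

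Three features of the protocol add weight:

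- The earlier repeat-dose human studies it describes lasted 10 days (section 1.4.2.1) and 4 weeks (section 1.4.2.3), so Days 43 to 85 lie beyond both.
- Section 1.4.1 reports "PF-04965842-related minimal to mild increases in serum transaminases" in rats and monkeys. The sponsor judged these not adverse, but they show that transaminases were a foreseeable thing to watch.
- The same panel feeds the creatinine re-test in Appendix 11.1 and the detection of potential Hy's law cases in section 8.6.2.

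**Working it through.** The plan states no figure on this point, so there is none to reproduce. The check is visit-day arithmetic.

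**Inputs**

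- Chemistry days up to the last dose: 1, 15, 43, 85 (Schedule of Activities; sections 6.2.1, 6.2.3, 6.2.5, 6.2.7).
- Hematology days up to the last dose: 1, 8, 15, 29, 43, 57, 85 (Schedule of Activities).
- Visit windows: ±1 day from Week 1 to Week 6, ±3 days from Week 8.
- Dosing: Days 1 to 85. Re-test: within 7 days.

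**1. Intervals between scheduled readings**

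| Panel | Intervals (days) | Sum | Longest | Longest, with windows |
|---|---|---|---|---|
| Chemistry | 14, 28, 42 | 84 | 42 (Day 43 to 85) | 42 − (1+3) = 38 to 42 + (1+3) = 46 |
| Hematology | 7, 7, 14, 14, 14, 28 | 84 | 28 (Day 57 to 85) | 28 − (3+3) = 22 to 28 + (3+3) = 34 |

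The chemistry gap is 42/84 = 50% of the time from first to last dose. Days 44 to 84 are 41 dosing days with no scheduled chemistry, 41/85 = 48% of dosing days.

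**2. How long the Week 6 sample can still act**

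An abnormal Day 43 result can be re-tested up to Day 43 + 7 = Day 50 and then stop treatment. From Day 50 to Day 85 is 35 days, or 35/42 = 83% of the gap, in which no scheduled chemistry result can start a stop. The Day 85 result comes on the day of the last planned dose and still needs confirmation.

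**3. Share of new abnormalities first tested on Day 85**

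Assume that onset is uniform over Days 1 to 85, that an abnormality persists until it is tested, and that there is no unscheduled testing. Then share = last interval / 84.

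- Chemistry: 42/84 = 50%.
- Hematology: 28/84 = 33%.

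Let the windows move in opposite directions, with the last dose moving with the Week 12 visit. Chemistry then ranges from 38/81 = 47% to 46/87 = 53%, and hematology from 22/81 = 27% to 34/87 = 39%.

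**4. Mean wait to the next scheduled reading**

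On the same assumptions, mean wait = (sum of squared intervals) / (2 × 84).

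- Chemistry: (14² + 28² + 42²)/168 = 2744/168 = 16.3 days.
- Hematology: (3 × 14² + 2 × 7² + 28²)/168 = 1470/168 = 8.8 days.

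**5. Dependence on the assumption**

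Without uniform onset, the chemistry share is simply the fraction of onsets after Day 43, and the hematology share the fraction after Day 57. If abnormalities arise mainly early, both fall towards zero; if mainly late, both rise towards one. The documents give no onset data from which to choose.

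**The case against.** The other side has a good deal to say, and much of it stands.

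- **The documents do not contradict each other on sampling.** The Schedule of Activities and the visit lists agree, and Appendix 11.2 sets action limits without promising a sampling frequency. This stands. The point is a mismatch between the stop rules and the monitoring schedule, not a conflict of text.
- **The stop rules remain in force.** A reader might infer that the chemistry rules are inoperative in the second half of treatment. The documents do not support that. A Week 6 abnormality can be confirmed and acted on until about Day 50. Unscheduled tests, visits and safety assessments are allowed (Schedule of Activities introduction, sections 7.3 and 7.5.2, Appendix 11). What remains is that this route needs a prompt.
- **The safety endpoint has more data than the three post-baseline samples taken during dosing.** A reader might infer that the incidence of liver test abnormalities rests on those three alone. It does not. SAP sections 5.2 and 7.4 include follow-up, so scheduled post-baseline chemistry falls on Days 15, 43, 85, 99 and 113. All arms share this schedule.
- **The re-test need not fall on a scheduled visit.** A reader might take the Week 13 list, "Obtain samples for laboratory testing: hematology and urine pregnancy test (female subjects of childbearing potential only", as breaking the one-week confirmation after an abnormal Day 85 result. Appendix 11.2 does not tie confirmation to a scheduled sample, and by then planned dosing is over.
- **Hematology has a gap too, and a reason for priority.** It also goes 28 days unread before Day 85. The psoriasis study found hematological and gastrointestinal adverse events the most common (section 1.4.2.3). This explains closer hematology monitoring. It does not explain leaving chemistry off the Week 8 draw.

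**Conclusion.** The point holds as a gap in scheduled monitoring. For 42 days (38 to 46 with windows), half of the time from first to last dose, four of the eight mandatory laboratory stop rows have no scheduled reading. For the last 35 of those days only an unscheduled test can trigger them before the last planned dose. These statements rest on visit days alone. The comparison of 50% for chemistry with 33% for hematology rests on uniform onset, persistence until tested and no unscheduled testing, so it shows scale and is not a forecast. Nothing here shows that a patient would be harmed, that the treatment comparison is biased, or that any particular testing interval is right. It is a specific and cheaply closed gap in safety monitoring that the protocol does not explain.

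**What to change.** Reconcile the Blood Chemistry row of the Schedule of Activities and section 6.2.6 with Appendix 11.2, so that the chemistry stop rows have a scheduled reading in the second half of dosing while treatment can still be stopped. Blood draws that already exist can serve, so no new visit or venipuncture is needed. How often to test is a clinical decision for the sponsor. If the present schedule is kept, the protocol should give the reason. Appendix 11.2 and the safety reporting should then state that these four rows have no scheduled reading between Day 43 and Day 85.

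The cost is an amendment to the schedule, an added serum tube and laboratory panel, and a small rise in the planned total blood volume (about 439 mL, section 7.5.1). Keeping the schedule and disclosing the gap costs only text.
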